## 6.9 Treatment phase

During the treatment phase, the patient is required to log into the Mictera app regularly and carry out the activities described for the day in question. Compliance with the set therapy goals is monitored via the Mictera app in pseudonymised form and reminders are communicated to the patient if necessary. The activity of app use is automatically documented.

The therapy is based on the principle of digital content, which includes personalised multimodal therapy with a focus on pelvic floor training, physiotherapy, mental training and

Kranus Health GmbH\_DINKS

behavioural therapy with methods of urinary urgency control and relaxation techniques. Another key component is the micturition diary, which patients can use to document their micturition behaviour. The approach includes several therapy programme elements whose effectiveness in the treatment of incontinence has been proven in the literature.

### 6.9.1 Micturition diary

Patients can document the amount they drink, meals, amount and frequency of micturition and symptoms. An algorithm helps with patient-individualised information. The visually simplified presentation helps patients to recognise correlations and motivate them.

### 6.9.2 Pelvic floor and physiotherapy exercises

The daily training consists of exercises focussing on the ability to repeatedly contract the pelvic floor muscles relevant for the function of the sphincter and the bladder reflex. The exercises are taught with the help of text, video instructions and interactive software elements. Special physiotherapy exercises for training the pelvic floor are suggested once a week. They are aimed at improving and supporting the pelvic floor. Here too, the exercises are taught with the help of text and detailed video instructions.

### 6.9.3 Bladder training / cognitive behavioural therapy

Behavioural therapy exercises are used to increase functional bladder capacity, reduce micturition frequency and urge problems. The patient therefore receives new content and goals in the app every week.

### 6.9.4 Mental exercises

- Mindfulness: Every week, patients receive new content on mindfulness-based approaches based on cognitive behavioural therapy strategies.
- Progressive muscle relaxation (PMR): The deliberate and conscious tensing and relaxing of certain muscle groups leads patients into a state of deep relaxation.
- Stimulus control methods: Unwanted thoughts such as the acute urge to urinate are acutely suppressed.
- All methods help patients to manage their symptoms and break through urge or urge conditioning. The content is provided in the form of audio sequences.

### 6.9.5 Acute urge control

In the event of a strong urge to urinate, the patient is given access to short versions of the structured exercises for mindfulness, PMR and thought control. They can also access a short pelvic floor training exercise or select a game to provide a situational distraction from the issue and gain control over the micturition reflex.

Kranus Health GmbH\_DINKS

### 6.9.6 Knowledge section /Nutrition section

Users receive daily educational content on the causes and underlying principles of incontinence. Another focus is on nutrition-specific correlations. General therapeutic measures are explained as well as psychological, habitual and organic correlations.

### 6.9.7 Further functions:

Participants have the opportunity to monitor the course of their symptoms and the progress of their therapy and are motivated by receiving progress awards.

### 6.10 Visits and analyses

During the 12-week treatment phase, no routine visits to the study centre are planned. However, if necessary, the patient can contact her gynaecologist, urologist, etc., the study centre or the study hotline at any time.

The study-specific surveys are listed in the ward round schedule (see **Table 1:** ward round schedule for the DINKS study).

### 6.11 End of study participation

The regular end of study participation for each study participant is after 12 weeks and completion of the questionnaire in week 12. Participation in the study is voluntary. Each participant has the right to withdraw from the study at any time at her own request, prematurely and without giving reasons (consent can also be withdrawn in this case) or to decide to discontinue treatment (no further treatment) without any disadvantages for her further (medical) treatment. In a follow-up period of 12 months after the primary survey period, the patient has the opportunity to take part in further surveys. Patients in both groups (arm A and B) are given the opportunity to continue using the app. During this time, the patient can contact her study centre, her treating gynaecologist, urologist or the study hotline at any time.

If a patient withdraws her consent and leaves the study, this constitutes a withdrawal from participation (WoC). If it is possible and the patient is willing to provide information, the study centre will attempt to find out the reason for the premature termination of the study. The participant is asked to state the reason for discontinuation, but is advised that she does not have to do so. It will be documented when and, if applicable, why she withdrew her consent.

### 6.12 End of the study

The planned end of the study is immediately after LPO.

Kranus Health GmbH\_DINKS

## 7 Adverse events

### 7.1 Complications and risks

Muscle and joint complaints due to the physical strain are possible side effects of the therapy programme. Serious injuries should not occur due to the exclusion criteria.

### 7.2 Recording and documentation of adverse events

### 7.3 Adverse event

An "adverse event", hereinafter referred to as "AE", is an adverse medical event, inappropriate patient management decision, illness or injury, or adverse clinical symptoms, including abnormal laboratory findings, in study participants in the clinical trial, even if not related to the product tested in the clinical trial.

### 7.4 Serious Adverse Event

The SAE according to ICH-GCP (serious adverse event) or "serious adverse event" refers to an adverse event that had one of the following consequences:

1. a patient management decision that has resulted in death or an immediate life-threatening situation for the subject or the death of the subject's offspring;
2. Death;
3. serious deterioration in the subject's state of health, which in turn had one of the following consequences:
  - a. life-threatening illness or injury;
  - b. Permanent physical injury or permanent impairment of a bodily function;
  - c. inpatient treatment or extension of the 's inpatient treatment;
  - d. Medical or surgical intervention to prevent a life-threatening illness or injury or permanent physical damage or permanent impairment of a bodily function;
  - e. chronic disease;
  - f. foetal endangerment, death of the foetus or congenital physical or mental impairment or birth defects.

### 7.5 Product defect or device-related adverse events

The "product defect" means an inadequacy in the identification, quality, durability, reliability, safety or performance of the product, including malfunctions, application errors or inadequacy of information provided by the manufacturer and will also be reported, documented and evaluated to the sponsor.

Adverse events are documented in the eCRF by the study centre after consultation with the patient. In addition, patients are contacted by telephone once after six weeks to ask about potential SAEs and AEs.

Kranus Health GmbH\_DINKS

All AEs and SAEs are documented in the eCRF in accordance with ISO14155. SAEs must be documented and transmitted to the sponsor within 24 hours of becoming known via the eCRF system (via eCRF and automatic e-mail from the eCRF to [[contact]](mailto:[contact])). The sponsor is then obliged to assess and report the SAE in accordance with its reporting obligations.

When using the Mictera therapy programme, the risk of undesirable side effects is generally very low. A comprehensive literature search was carried out for the authorisation as a medical device and for the study protocol. No relevant risks were described when carrying out the corresponding exercises.

## 7.6 Definition of the risk threshold

### 7.6.1 Risk threshold for patients

Patients should not have SAEs due to the use of Kranus Mictera or need to see a doctor due to this digital therapy.

For the study, a contact is made after 6 weeks within the 12-week therapy with Kranus Mictera as part of the monitoring of SAEs of study participants. If the patient reports an SAE during the course of the study, or if the patient has to see a doctor as a consequence of using Kranus Mictera, this is documented in the eCRF (including an automatic e-mail to [[contact]](mailto:[contact])) and the sponsor assesses whether there is a connection with the use of Kranus Mictera. If there is a connection with the digital therapy, will be evaluated whether further participation in the study is justifiable for the patient.

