### 7.6.2 Risk threshold for the study

The study should not cause more than five identical or similar SAEs due to the use of Kranus Mictera.

The sponsor is informed of (S)AEs via eCRF and [[contact]](mailto:[contact]) and monitors and assesses the SAEs that occur. If more than five SAEs occur, which firstly are directly related to the product and secondly have the same or a similar cause after assessment, it is assumed that the risk threshold for the study exceeded and the study is discontinued.

If necessary, the product "Kranus Mictera" can be withdrawn from the market immediately. In the event of serious risks, the sponsor shall also immediately inform the competent authorities and, where appropriate, the notified body that issued the certificate of conformity, providing in particular details of the non-conformity and of any corrective action already taken.

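### Section 7.6 rests SAE relatedness on the sponsor's judgement; no causality judgement by the study centre is stated to count toward the continuation review or the stopping rule

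*Combined protocol and SAP*

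**What the plan says.** Section 7.5 divides the work. On the centre's side, "Adverse events are documented in the eCRF by the study centre after consultation with the patient". On the standard, "All AEs and SAEs are documented in the eCRF in accordance with ISO14155". On timing, "SAEs must be documented and transmitted to the sponsor within 24 hours of becoming known via the eCRF system", after which the sponsor has to assess the SAE and report it.

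Section 7.6.1 sets the patient-level rule. When an SAE is reported, or a doctor's visit results from using the app, the event is documented and "the sponsor assesses whether there is a connection with the use of Kranus Mictera". It continues: "If there is a connection with the digital therapy, will be evaluated whether further participation in the study is justifiable for the patient". No role is named for that second step.

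Section 7.6.2 sets the study-level rule. The sponsor "monitors and assesses the SAEs that occur", and the study is discontinued if there are more than five SAEs "which firstly are directly related to the product and secondly have the same or a similar cause after assessment". It adds: "In the event of serious risks, the sponsor shall also immediately inform the competent authorities and, where appropriate, the notified body".

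**The concern.** Relatedness is the input to both safety rules. It opens the review of whether a patient should continue, and it is one of the two conditions an SAE must meet to count toward stopping the study. The only named judge has an interest in the answer. Section 10.5 says the sponsor finances the study. The app carries the sponsor's name, and the duty toward the notified body in 7.6.2 suggests that it is also the manufacturer.

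The text names no independent safety body, and section 9.4 plans no monitoring. The centre consults the patient about the event, yet its view on cause has no stated effect. If the sponsor rates an event unrelated and the centre would have rated it related, nothing in 7.6 brings that disagreement to light. A later statement that no related SAEs occurred would then rest on one interested assessor.

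**Working it through.** The plan gives no figure to reproduce. The check is a reading of every place where a causality judgement could be assigned, followed by the logic of the proposed counting rule.

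**Step 1: who judges what**

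| Place | Centre or investigator | Sponsor |
|---|---|---|
| 7.2 | heading only, no text | heading only, no text |
| 7.5 | documents AEs after talking to the patient | receives SAEs within 24 hours, assesses and reports them |
| 7.6.1, relatedness | not named | judges the connection with the app, stated outright |
| 7.6.1, continued participation | no role named | no role named |
| 7.6.2 | not named | monitors and assesses SAEs |
| 1.5, visit scheme | AE recording scheduled, no causality item | none |
| 6.10 | patient may contact the centre | none |
| 8.11 | AEs and SAEs listed, no assessor given | none |

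Only 7.6.1 gives relatedness to the sponsor in so many words. Section 7.5 uses the general term for assessment. Section 7.6.2 speaks of assessing SAEs and then applies a threshold that requires relatedness. The sponsor is the only assessor named in any of the three.

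**Step 2: what the stopping rule needs**

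More than five means 6 or more. Let S be the number of SAEs of the same or similar cause that the sponsor rates related. Let I be the number of SAEs of that cause that only the investigator rates related.

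- Current wording, taking the sponsor as sole assessor: stop if S ≥ 6.
- Either-party rule: stop if S + I ≥ 6.

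Since I ≥ 0, S + I is never below S, so the count can rise but cannot fall. The two rules differ only when S ≤ 5 and I ≥ 6 − S. With S = 5 a single investigator-only rating is enough (6 − 5 = 1). With S = 0 six are needed (6 − 0 = 6).

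**Step 3: scale**

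If each SAE occurs in a different woman, six SAEs are 6/99 = 6.1% of the planned intervention arm. If all 198 women eventually use the app, because controls gain access after week 12, six are 6/198 = 3.0%. Section 7.5 describes the risk of side effects as very low, so reaching six looks unlikely under either rule.

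Turning this into a probability would need the rate of related SAEs and the rate at which investigator and sponsor disagree. The documents give neither, so none is claimed.

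**Step 4: the patient-level rule**

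This rule has no threshold. One SAE rated related opens a continuation review. A single investigator-only rating would therefore change what happens to that patient, so the second judgement is more likely to matter here than in the stopping rule.

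**The case against.** The strongest objection is that this argues from places that cannot be read. Section 1.1 (persons and bodies involved) and the eCRF form were not available for this review, and 7.5 ties AE documentation to ISO14155. An investigator causality field may already exist. That stands, and a reader who infers that no investigator ever rates causality, or that the protocol breaches the standard it cites, goes further than the documents allow. What remains is that 7.6 rests on the sponsor's assessment and does not say that any centre entry counts.

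Second, the passive phrases in 7.6.1 and 7.6.2 do not exclude the centre. The doctor-visit trigger in 7.6.1 also implies that someone has attributed the visit to the app before the sponsor looks at it. Both are true. But that trigger concerns doctor's visits rather than SAEs as such, its actor is unnamed, and the relatedness judgement that follows is still the sponsor's.

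Third, a reader might infer that the sponsor alone controls whether a patient continues, or that serious risks could go unreported. Neither is supported. The patient can contact the centre, her own doctor or the hotline (6.10) and can leave at any time (6.11). The duty to inform authorities is explicit in 7.6.2, and individual events are listed in the report (8.11).

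Fourth, the gain in independence is modest. There is one centre, and section 9.1 has it informing patients on the sponsor's behalf. That also stands. A second recorded opinion from those who spoke to the patient is still better than none.

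**Conclusion.** The point holds in a limited form. Section 7.6.1 assigns relatedness to the sponsor, 7.5 and 7.6.2 name no other assessor, and no centre judgement is stated to count toward either rule. This is a design choice worth improving rather than an error, and the change is optional.

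The effect on whether the study stops is probably small, given the threshold of six and the low risk described in 7.5. That is a judgement, not a calculation. The effect on individual continuation reviews cannot be estimated. Efficacy results are unaffected.

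The conclusion assumes that neither section 1.1 nor another study document gives the investigator a causality rating that feeds 7.6. If one does, only the wording of 7.5 and 7.6 needs to change. That the sponsor makes the app is inferred from its name and the notified-body duty; that it finances the study is stated.

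**What to change.** **Section 7.5.** State that the study-centre investigator records relatedness for every SAE in the eCRF, independently of the sponsor. The entry may follow the initial report, so the 24-hour transmission is not delayed. Apply this to SAEs already recorded as well.

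**Sections 7.6.1 and 7.6.2.** Treat an SAE as related if either the investigator or the sponsor rates it so, and document disagreements. In 7.6.1 this opens a continuation review and is not automatic withdrawal. In 7.6.2 leave the more-than-five threshold and the same-or-similar-cause criterion unchanged.

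**Cost.** One eCRF field if none exists, otherwise wording only, at the single centre that already documents these events. Version 2.1 is dated 14.11.2024, after the planned end of recruitment on 31.10.2024. The change would therefore touch a live data system and require rating of existing SAEs. The visit scheme records AEs up to week 48, so there is still time for it to be useful.

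**Downside.** The related count can rise but not fall, by an amount the documents do not allow one to estimate, and more continuation reviews may be held.

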### 7.6.2 Risk threshold for the study

The study should not cause more than five identical or similar SAEs due to the use of Kranus Mictera.

The sponsor is informed of (S)AEs via eCRF and [[contact]](mailto:[contact]) and monitors and assesses the SAEs that occur. If more than five SAEs occur, which firstly are directly related to the product and secondly have the same or a similar cause after assessment, it is assumed that the risk threshold for the study exceeded and the study is discontinued.

If necessary, the product "Kranus Mictera" can be withdrawn from the market immediately. In the event of serious risks, the sponsor shall also immediately inform the competent authorities and, where appropriate, the notified body that issued the certificate of conformity, providing in particular details of the non-conformity and of any corrective action already taken.

### 7.6.3 Onset of pregnancy

The occurrence of pregnancy is considered an adverse event (AE) in this clinical trial for safety reasons. If a pregnancy is reported, the patient will be excluded from the study as soon as it becomes known and access to the Kranus Mictera app will be withdrawn.

Kranus Health GmbH\_DINKS

## 8 Statistics

### 8.1 Endpoints

The time point of interest for the target evaluation is after 12 weeks, i.e. the end of study for intervention arm A and the delayed start of the intervention in control arm B.

### 8.2 Primary endpoint

- 1) Relative change (rel-CfB-IEF) of the IEF from baseline to week 12 in relation to baseline

### 8.3 Secondary endpoints

- 2) Change in ICIQ-SF from baseline to week 12
- 3) Change in I-QOL from baseline to week 12
- 4) Change in the PAM-13 questionnaire from baseline to week 12
- 5) PGI-I questionnaire (overall improvement after treatment) at the end of the study
- 6) Proportion of patients without incontinence (cured patients) at the end of the study
- 7) Reduction in micturition frequency during the day
- 8) Reduction in micturition frequency at night
- 9) Reduction in pad consumption
- 10) Reduction of the imperative urge to urinate
- 11) Change in functional bladder capacity
- 12) Reduction in body weight
- 13) Reduction in the proportion of patients with treatment failure within the study period
- 14) Proportion of patients with at least 50% reduction in IEF from baseline to week 12
- 15) Reduction in the frequency of stress incontinence episodes in the S/U-IQ
- 16) Reduction in the frequency of urge incontinence episodes in the S/U-IQ

### 8.4 Planning the scope of the study (case number planning)

Randomised: Arm A to Arm B in a 1:1 ratio

Planning the scope of the study for comparisons between the groups:

- IEF: Relative reduction in incontinence episodes (rel-CfB-IEF) with desired improvement of 50%, Minimum Important Difference (MID) approx. 50% from Yalcin 2010; at  $d/s = 0.7$  with significance level  $\alpha = 5\%$  2-sided and power  $1 - \beta = 90\%$ :  $N = 2 \times 44 = 88$ , + 20% due to drop outs and their conservative imputation as well as subgroup analyses:  $N = 120$ .
- ICIQ-SF: CfB with desired improvement by  $d = 2.9$  vs. control (MID = 2.5 from Nyström 2014 and Asklund 2017) by  $d/s = 2.9/3.2 = 0.9$  with  $\alpha = 5\%$  2-sided and power  $1 - \beta = 90\%$ :  $N = 2 \times 28$ .
- I-QOL: CfB with desired improvement by 6.3 vs. control (MID= 6.3 from Yalcin 2006) by  $d/s = 6.3/14 = 0.45$  (with  $\alpha = 5\%$  2-sided and power = 80%:  $N = 2 \times 90$ ).

Kranus Health GmbH\_DINKS

- PAM-13: CfB with desired improvement by 6 points vs. control (MCID= 6, i.e. approx. 15% of the PAM rank from 13 - 52 and from John, 2020) by  $d/s = 6/12 = 0.5$  (with  $\alpha = 5\%$  2-sided and power = 80%:  $N = 2 \times 64$ ).

Due to drop-outs and their conservative imputation, the total number of cases is set at 2 x 99 study participants for the evaluation of the primary endpoints.

## 8.5 Discussion of the end points

Primary and secondary endpoints for urinary incontinence are not uniformly defined in the literature and are used heterogeneously in the various studies [30, 4, 31].

In principle, a distinction can be made between so-called subjective (based on questionnaires) and objective (number of incontinence episodes, pad tests) [32].

Both types of endpoints are used in studies as the primary "outcome variable" and accepted.

## 8.6 Primary endpoint

There is no standardised method for measuring incontinence episodes. In a study very similar to ours (app-based pelvic floor muscle training for stress incontinence), the incontinence episodes were measured in the micturition diary on 2 days and then multiplied by 3.5 to obtain a weekly average [8]. In a similar, internet-based pelvic floor training study, Sjöström et al. used an analogue measurement system [33]. In a study with different conservative measures (including pelvic floor muscle training), Bo et al. the incontinence episodes over 3 days [34]. Castro et al [35] measured incontinence episodes over 7 days in a similar study.

In the present study, incontinence episodes were measured over 3 days (baseline and end-of-study), the mean value per day was calculated and this was used as the primary endpoint.

There is a lack of data in the literature on the minimum clinically relevant difference (MID) in connection with specific measures such as medication or pelvic floor muscle training. In general, a reduction of 50% is described as clinically relevant for conservative measures for incontinence [6, 31]. Based on the literature, we define a reduction in incontinence episodes as the quantitative primary endpoint.

Statistically analysed is primarily the relative change ( $rel-CfB-IEF = CfB/B$ ) of the IEF from baseline to week 12 in relation to baseline; desired reduction of the mean relative IEF by 50% versus control; IEF frequency = mean value of IEs over 24 hours calculated from IEs over 72 hours.

